7.8 Analysis of safety and tolerability

7.8.1 Adverse events

Adverse events (AEs) and adverse drug reactions (ADRs) reported after administration of the study treatment will be classified by system organ classes (SOC) and preferred terms using the MedDRA dictionary (version 18.1). An ADR is defined as an AE to which the study treatment is assessed to be related to study drug by the investigator.

The number and proportion (%) of subjects having each AE or ADR will be given by treatment group. The numbers and proportions will be additionally broken down by severity (mild, moderate, severe) and by the causality (definitely not related, unlikely to be related, possibly related, probably related, definitely related) and gluten challenge (defined as before gluten challenge and on or after gluten challenge). In addition, the number of events and their proportion (%) of the total number of events can be tabulated. All AEs and SAEs will also be listed.

Additionally, narrative descriptions will be included in the study report for all SAEs and AEs leading to discontinuation of the treatment.

Any symptoms recorded before entry to the study, which remained unchanged or improved, will be followed and evaluated separately from the AEs. If the severity of a symptom increases during the study, the symptom will be considered an AE and it will be reported in the AE section.

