- To assess the safety and tolerability of AMG 714 when administered to adult patients with celiac disease exposed to a gluten challenge.

The **safety endpoints** of the study are:

- Adverse events (AEs);
- Clinical laboratory tests;
- Physical examination;
- Vital signs;
- Immunogenicity.

Clinical laboratory tests -including immunogenicity-, physical examinations and vital signs will be tabulated by time point and treatment group and reviewed for potential safety signals. All adverse events (AEs) and serious adverse events (SAEs) will be listed and tabulated by treatment group, system organ class (SOC), preferred term (PT) and further by severity and relatedness to the study drug.

The **exploratory objectives** of the study are:

- To assess the pharmacokinetics (PK), pharmacodynamics (PD), and PK/PD associations of AMG 714.

The **exploratory endpoints** of the study are:

- PK;
- PD, including
 - Physician Global Assessment of Disease (PGA);
 - Biomarkers of disease activity;
 - Celiac Disease Patient-Reported Outcome (CeD PRO);
- Exposure/Response (PK/PD).

PK data will be tabulated by treatment group. In addition, dose proportionality, achievement of steady-state, and accumulation ratio based on C_{trough} concentrations, comparison of C_{trough} levels with corresponding values in study 20060349, and correlation of C_{trough} concentrations with biomarkers of disease activity will be evaluated. Exploratory PD endpoints are Physician Global Assessment of Disease (PGA), biomarkers of disease activity (i.e., CRP, serum IL-15 [sIL-15]) and Celiac Disease Patient Reported Outcome (CeD PRO). The exploratory PD endpoints will be evaluated by investigating the change from baseline and weekly scores, if applicable, of AMG 714 dose arms and placebo arm. PK/PD association will mainly be assessed graphically.

PK analyses will be described in detail in a separate PK Data Analysis Plan (DAP) to be prepared by Celimmune.

In subjects with dermatitis herpetiformis (DH), optional photography will be conducted according to the study manual. Skin biopsies will be allowed per investigator's discretion but will not be part of this protocol. Any skin information on DH will be summarized by Celimmune for descriptive purposes without formal statistical analysis.

3 Study type and design

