CELIM-NRCD-001 is designed to be a Phase 2a randomized, double-blind, placebo-controlled, parallel-group study to evaluate the efficacy and safety of AMG 714 for the attenuation of the effects of gluten exposure in adult patients with celiac disease during a gluten challenge.

After signing consent subjects will be screened for the study. All subjects who meet the study entry criteria will be randomized at a 1:1:1 ratio to receive 150 mg or 300 mg AMG 714 or placebo once every two weeks for 10 weeks. Randomization will be stratified by site and sex. The study drug (AMG 714 or placebo) will be administered at the clinical site in a double-blind fashion via subcutaneous (SC) injection. Subjects will remain confined to the study site for a minimum of 1 hour after each administration of study medication. During this time the Investigator and study site staff will assess the subject for AEs and collect the required PK samples and post dose vital signs as outlined in the study schedule of events in [Appendix 1](#).

In addition to receiving study medication (AMG 714 or placebo), all subjects will be required to consume either placebo gluten or active gluten administered in a single-blind fashion. Beginning on the day following Visit 1 (i.e. Week 0/Day 1, since Visit 1 is defined as Week 0/Day 0) through Visit 2 (Week 2/Day 14), all randomized subjects will consume placebo gluten, in the form of gluten-free foodstuffs (e.g. rusks) provided by the Sponsor, twice a day (BID) at the time of two regularly consumed gluten-free meals (chosen by the subject). Starting at Visit 2, subjects will switch to consume a daily total of approximately 2-4g of active gluten, provided in the form of foodstuff identical in appearance to that provided during the two-week single-blind placebo-gluten period. These gluten-containing foodstuffs, supplied by the sponsor, will be consumed in approximately 1-2g doses BID at the time of two regularly consumed gluten-free meals (as chosen by the subject) from Visit 2 (Week 2/Day 14) through the end of the treatment period at Visit 7 (Week 12/Day 84). Consumption of additional products containing gluten will be prohibited and subjects will be expected to continue total adherence to their former GFD from the time of screening until the follow-up study visit (Visit 8, Week 16/Day 112).

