Subjects' adherence to GFD and consumption of provided gluten will be periodically assessed via stool and urine sample testing using the iVYELISA GIP stool and urine gluten tests. Subjects with known or suspected GFD transgressions or those suspected of non-compliance to protocol specified gluten dosing will be counselled and allowed to continue in the study.

A study site staff member will contact each subject by telephone both one day and one week after the first study drug administration in order to assess for AEs. Subjects will return to the clinic every two weeks for study drug administration and/or efficacy and safety assessments as indicated in the study schedule of events in [Appendix 1](#). The final study drug administration will occur at Visit 6 (Week 10/Day 70). An end-of-study efficacy assessment

will be collected at Visit 7 (Week 12/Day 84). A final study visit will be conducted six weeks after the last administration of study drug at Week 16 (Visit 8/Day 112).

Subjects who meet all other study entry criteria will undergo upper gastrointestinal endoscopy and biopsy prior to baseline (Visit 1, Week 0/Day 0) and at the end of the 12-week randomized period while still on the gluten challenge within five days before Visit 7 (Week 12/Day 84) in order to assess changes from baseline in VH:CD ratio, IELs, and Marsh score.

If the screening biopsy shows villous atrophy with a VH:CD less than 1.5 (1.4 or lower), and after notification to the sponsor, the subject may be allowed to stay in the study but the gluten challenge will not be started (or will be interrupted if the patient has been started in the challenge) and the subject will be analysed separately for the main efficacy assessments (primary and secondary endpoints). Subjects with VH:CD 1.5 or above will receive the gluten challenge.

[figure not shown]

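### Splitting AEs only into before and on-or-after gluten challenge cannot separate a gluten effect from longer observation, pools four off-gluten weeks, and gives no rule for never-challenged or interrupted subjects

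*SAP*

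**What the plan says.** Section 7.8.1 of the SAP covers AEs "reported after administration of the study treatment". The main statistic is a raw proportion: "The number and proportion (%) of subjects having each AE or ADR will be given by treatment group". It is further broken down by severity, by causality and by "gluten challenge (defined as before gluten challenge and on or after gluten challenge"). Event counts may be added as a share of all events. The section plans no rate per unit of time and states no denominator specific to a period.

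Section 3 gives the timeline. Visit 1 is Day 0, and placebo gluten is eaten for the first two weeks. Then "Starting at Visit 2, subjects will switch to consume a daily total of approximately 2-4g of active gluten", and this continues "from Visit 2 (Week 2/Day 14) through the end of the treatment period at Visit 7 (Week 12/Day 84"). On the end of follow-up it says: "A final study visit will be conducted six weeks after the last administration of study drug at Week 16 (Visit 8/Day 112"). AEs are monitored throughout the study.

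Section 3 also provides for subjects whose screening biopsy falls below the VH:CD threshold. They may stay in the study, but "the gluten challenge will not be started (or will be interrupted if the patient has been started in the challenge"). For efficacy, sections 3 and 7.1 separate them through PP1 and PP2. For safety, section 7.1 and Table 1 use the ITT set, which includes them.

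Section 2 states the secondary objective: "To assess the safety and tolerability of AMG 714 when administered to adult patients with celiac disease exposed to a gluten challenge".

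**The concern.** In the text available, this breakdown is the only planned summary that relates AEs to gluten. The subgroup analyses in section 7.9, including those on gluten consumption, may be confined to histology endpoints. A reader who wants to know what happened on gluten has only these two columns, and three features make them hard to use:

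- **Unequal time.** The columns hold percentages of subjects with an event, which rise with time at risk, and the times differ greatly.
- **Mixed exposure.** The second column holds weeks on gluten and weeks after gluten. The weeks that bear on the secondary objective cannot be read off by themselves.
- **Undefined membership.** A subject who never starts the challenge fits neither label. A subject who starts and is interrupted falls literally under on-or-after for all later time, whether or not any gluten is still eaten. The plan decides neither case, so whoever programs the table will have to.

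At stake is the interpretability of a secondary safety summary. No test or primary result is affected.

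**Working it through.** The SAP gives no figure to reproduce here. The check is of window lengths and what they imply.

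**Inputs from the SAP.** First dose Day 0 (six doses two weeks apart, the last on Day 70: 70 − 5 × 14 = 0). Active gluten from Day 14 to Day 84. Final visit Day 112. About 21 subjects per arm (section 6).

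**Assumed inputs.** The SAP gives no AE rate. I take a constant rate r of 0.01 to 0.20 per subject-week, full follow-up, and no gluten effect. It gives no number of never-challenged subjects either, only that they are a small fraction. I take k = 0 to 3 per arm.

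**Step 1, window lengths.** Before: 14/7 = 2 weeks. On gluten: (84 − 14)/7 = 10 weeks. After gluten: (112 − 84)/7 = 4 weeks. On-or-after is therefore 10 + 4 = 14 weeks, 7 times the before window. Of those 14 weeks, 4 (29%) are off gluten.

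**Step 2, percentage with at least one AE when gluten does nothing.** The expected proportion over t weeks is 1 − exp(−r·t).

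| r per week | before (2 wk) | on-or-after (14 wk) | ratio |
|---|---|---|---|
| 0.01 | 2.0% | 13.1% | 6.6 |
| 0.02 | 3.9% | 24.4% | 6.2 |
| 0.05 | 9.5% | 50.3% | 5.3 |
| 0.10 | 18.1% | 75.3% | 4.2 |
| 0.20 | 33.0% | 93.9% | 2.9 |

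Expected event counts differ by the full factor of 7. Events per subject-week have a ratio of 1.0 at every r.

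**Step 3, effect of pooling the off-gluten weeks.** Suppose one arm stays at the background rate, and the other has twice that rate on gluten and returns to background when gluten stops. The true on-gluten ratio is 2.0. Over the pooled window it is (10 × 2 + 4 × 1)/14 = 24/14 = 1.71. A ratio of 1.5 becomes 1.36, and 3 becomes 2.43. The same arithmetic applies to on-gluten against background within one arm.

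**Step 4, never-challenged subjects.** If all 16 of their weeks are counted as before, the ratio of expected event counts is (21 − k) × 14 / [(21 − k) × 2 + 16k]. For k = 0, 1, 2, 3 this gives 7.0, 5.0, 3.8, 3.0. Their placement therefore moves the table materially, and it moves it opposite to step 2, shrinking the excess.

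**Step 5, whether three periods alone would be enough.** On gluten against before is 10 weeks against 2. With no gluten effect the raw percentages still differ, by a factor of 4.8 at r = 0.01 and 2.6 at r = 0.20. Rates are needed as well as the third period.

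**The case against.** The strongest reply is that the table is descriptive. Section 7.8.1 plans no contrast, estimate or test of before against on-or-after. The results are given by arm, and the safety objective concerns AMG 714, so the contrast that matters is drug against placebo. Randomised arms share the same planned windows, so the 2-to-14 imbalance does not bias that contrast within a level. All of this stands.

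A reader might infer that the table will show a gluten effect where none exists. The document does not support that. The excess in step 2 arises only if someone compares raw columns within an arm, and the absence of a gluten effect is a condition of the calculation, not something the SAP tells us. Nor do the three features act together to create the excess: counting never-challenged subjects as before reduces it, and the off-gluten weeks lengthen the window while diluting a true effect on the rate scale.

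It can also be said that on-or-after is naturally read as onset relative to challenge start, so the pooling is disclosed and post-challenge AEs are not mislabelled, and that all AEs are listed individually. That is fair, but disclosure does not let a reader take the on-gluten weeks out of the summary. The dilution in step 3 applies to drug against placebo too, though its size depends on how quickly the rate falls once gluten stops, which the SAP does not say.

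Finally, the table templates (Appendix 4) are not available here and may contain a further category or denominator. If so, they would depart from the two levels that section 7.8.1 defines, and the text should be brought into line.

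**Conclusion.** The point holds as a limit on what the planned table can show. The two-level rule compares about 2 weeks with about 14, mixes 4 off-gluten weeks into the second level, and gives no rule for subjects whose challenge is never started or is interrupted. These facts follow from the SAP alone.

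The sizes rest on assumptions. A 3- to 7-fold raw excess without any gluten effect needs a constant rate between 0.01 and 0.20 per subject-week and full follow-up. Dilution of a ratio from 2.0 to about 1.7 needs an immediate return to background when gluten stops. The influence of never-challenged subjects depends on a number that the SAP does not give.

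The randomised comparison within a level is not biased by the unequal windows. For that comparison, the remaining weaknesses are the pooled off-gluten weeks and the undefined placement of some subjects. This is a cheap improvement to a descriptive safety summary.

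**What to change.** In section 7.8.1, replace the two levels by three, set from each subject's actual first and last active-gluten dates:

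1. before active gluten;
2. on active gluten;
3. after active gluten, to Week 16.

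Use the subjects who enter each period as its denominator, and print events per subject-week beside the percentages. Show never-challenged subjects in a separate column. Assign interrupted subjects' time by their actual gluten dates. State that the on-gluten period is the one used to compare arms for the secondary objective.

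The cost is SAP wording and a changed table layout. AE onset and gluten-start dates are already needed for the two-level split, so the last gluten date is the only extra item. The table becomes wider, and with about 21 subjects per arm some cells will be sparse, the never-challenged column above all.

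One limit remains and should be footnoted. Of the six doses, one falls on Day 0 and five on Day 14 or later. In the active arms, differences between the before and on-gluten periods therefore stay confounded with repeated dosing and should not be read as a pure gluten effect.

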7.8.2 Clinical laboratory tests

Clinical laboratory tests include haematology, clinical chemistry, and urinalysis panels. The complete list of clinical laboratory parameters is presented in Table 3 below.

Table 2 Clinical laboratory tests

Haematology	Clinical Chemistry	Urinalysis
Basophils (% and absolute)	Alanine Aminotransferase (ALT)	Blood Cells (Erythrocytes, Leukocytes)
Eosinophils (% and absolute)	Albumin	Glucose
Haematocrit	Alkaline Phosphatase	Ketones
Hemoglobin	Aspartate Aminotransferase (AST)	Microscopic evaluation
Lymphocytes (% and absolute)	Bilirubin (Total)	Protein/Albumin
Monocytes (% and absolute)	Blood Urea Nitrogen (BUN)	
Neutrophils (% and absolute)	Calcium	
Platelet Count	Chloride	
Red Blood Cell (RBC) count	Creatinine	
White Blood Cell (WBC) count	Glucose	
	Lactate dehydrogenase (LDH)	
	Potassium	
	Protein (Total)	
	Sodium	

Clinical laboratory parameters will be obtained at times indicated in the study schedule ([Appendix 1](#)). Blood and urine samples collected at the Screening Visit will require a minimum 8-hour fast.

All clinically significant findings during the study should be followed until resolution or until the finding is clinically stable. Subjects may be withdrawn from study drug if the Investigator or Sponsor deems the clinically significant finding compromising to the subject's safety; however, these subjects will continue to be followed-up per protocol, unless consent is withdrawn.

Detailed information regarding the collection and handling of clinical laboratory specimens, including blood draw totals for each visit and instructions for re-testing of missing or compromised specimens, can be found in a separate Specimen Collection and Processing Manual or equivalent document supplied by the Sponsor.

Laboratory test values will be presented by individual listings with flagging of values outside the normal ranges (normal ranges will be presented in statistical analysis report appendix). Absolute laboratory values and changes from baseline will be presented using summary statistics by treatment group and visit. Clinical laboratory variables will also be explored in individual and mean curves. ITT analysis population will be used.

7.8.3 Physical examination

Physical examination will be performed at times indicated in the study schedule ([Appendix 1](#)) and includes an examination of general appearance; head, eyes, ears, nose, throat (HEENT); lymph nodes; respiratory; cardiovascular; gastrointestinal; musculoskeletal; neurological, psychological and dermatological systems.

Physical examination results will be tabulated by treatment group, visit, body system, result (normal, abnormal, not done) and clinical significance (yes, no) and listed using ITT analysis population.

7.8.4 Vital signs

Vital signs include body temperature, pulse rate, systolic blood pressure (sitting), diastolic blood pressure (sitting), and respiratory rate. BMI and BSA will be obtained from measurements of body weight and height. Vital signs will be measured at screening and all other study visits.

Vital signs will be listed and changes from baseline and absolute values will be presented using summary statistics by treatment group and visit. Individual and mean absolute values and change from baseline values in weight will also be presented graphically by time point and treatment group.

ITT analysis population will be used for the analysis of vital signs.

7.8.5 Immunogenicity

Immunogenicity, i.e. the generation of anti-drug antibodies (ADA), is a potential risk for any biologic therapeutic. Immunogenicity may lead to injection reactions and to loss of efficacy when the antibodies are neutralizing and high-titer.

A two-tiered immunogenicity testing approach will be used in order to determine if a sample contains ADAs. Samples will be initially tested in an immunoassay. Samples that test positive for binding antibodies will then be tested in an assay to detect neutralizing antibodies (NAb). Immunogenicity testing will be performed at times specified in schedule of study procedures ([Appendix 1](#)).

Immunogenicity will be tabulated by treatment group, visit, ADA test result (negative, positive) and neutralizing antibodies test result (negative, positive) and listed. ITT analysis population will be used.

7.8.6 Other safety variables

7.8.6.1 Pregnancy test

All females of child bearing potential (FOCBP) will have urine or serum pregnancy tests throughout the study as outlined in schedule of study procedures ([Appendix 1](#)). Subjects who become pregnant during the study will be withdrawn from participation and the outcome of the pregnancy followed.

Pregnancy test results will be listed by treatment group, visit, test type (serum, urine) and result (negative, positive). ITT analysis population will be used for presenting pregnancy test results.

7.8.6.2 Prior and concomitant medications

Prior and concomitant medications will be collected throughout the study and coded using the World Health Organization Drug Dictionary (WHO DD) 2014 September version.

Prior and concomitant medication will be listed for ITT analysis population.

7.9 Additional analyses

In addition to the main analyses, pre-specified subgroup analyses may include the following, if reasonable distributions of subgroups are available for statistically meaningful assessments:

- Dietary transgressions (insufficient or excessive gluten consumption) based on serial iVYLISA GIP testing;
- Sex;
- Site;
- Baseline histology and serology;
- Expression of certain biomarkers at baseline, such as CD122, Granzyme B and IL-21R in IELs, or IL-15 in serum.

These additional sensitivity analyses may be carried out only for histology endpoints (i.e., the primary and secondary efficacy endpoints dependent on biopsy tissue). Separate models will be fitted for males and females, compliant and non-compliant subjects, and for each site. In order to determine whether the effects of sex, compliance and site are statistically significant, additional three models are fitted where compliance, sex and site and their interaction terms with treatment group, respectively, are included.

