RBC	Red blood cell
RCD-II	Type II Refractory Celiac Disease
RE	Role limitations due to emotional problems
SAE	Serious adverse event
SAP	Statistical analysis plan
SC	Subcutaneous
sCD3-	Surface CD3-negative
sCD8-	Surface CD8-negative
SD	Standard deviation
SOC	System organ class
ULOQ	Upper limit of quantification
UN	Unstructured
VT	Vitality
VH:CD	Villous height to crypt depth ratio

WBC White blood cell

WHO DD World Health Organization Drug Dictionary

1 Introduction

This is a statistical analysis plan (SAP) for study CELIM-NRCD-001 which is based on the final study protocol CELIM-NRCD-001 Version 3 (dated 29AUG2016). This SAP describes the statistical analyses which will be presented in the clinical study report.

2 Study objectives

The study objectives are the following:

The **primary objective** of the study is:

- To assess the efficacy of AMG 714 in attenuating the effects of gluten exposure in adults with celiac disease.

The **primary efficacy endpoint** is:

- Attenuation of gluten-induced small intestinal mucosal morphological injury, measured morphometrically as villous height to crypt depth (VH:CD) ratio.

The primary endpoint of the study is the difference in the Baseline-to-Week-12 % change of VH:CD ratio between each of the two AMG 714 dose arms against the placebo arm.

The **secondary efficacy endpoints** of the study are:

- Attenuation of gluten-induced small intestinal mucosal inflammation measured as intraepithelial lymphocyte (IELs) density;
- Attenuation of gluten-induced small intestinal mucosal morphological injury using a grouped classification of Marsh score;
- Attenuation of gluten-induced serum antibodies (i.e. anti-tissue transglutaminase antibodies [anti-tTG] IgA, anti-deamidated gliadin peptide antibodies [anti-DGP] IgA and IgG);
- Attenuation of gluten-induced clinical symptoms (i.e. Bristol Stool Form Scale [BSFS], Gastrointestinal Symptom Rating Scale [GSRS] and celiac disease GSRS [CeD-GSRS]).

The secondary endpoints of Marsh score and total IEL counts will be evaluated by the change from baseline to Week 12 between the two AMG 714 dose arms and the placebo arm. Anti-tTG IgA, anti-DGP IgA and IgG will be evaluated by comparing the change from baseline in results obtained after every four weeks of two AMG 714 dose arms and placebo arm. BSFS, GSRS and CeD-GSRS will be evaluated by comparing the change from baseline in weekly scores of two AMG 714 dose arms and placebo arm.

The **secondary objective** of the study is:

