The baseline and post-baseline weekly total CeD PRO scores along with the change from baseline values will also be described by summary statistics and tabulated by treatment group. Change from baseline for the weekly CeD PRO scores of individual questions (calculated as the average score of a question within a week) will also be tabulated by week and treatment group and described by summary statistics. The scores of individual questions and the total daily CeD PRO scores will be listed, as well as the total and by question weekly CeD PRO scores. Individual and mean curves of both the total weekly and daily CeD PRO scores as well as the individual questions will also be plotted by time point and treatment group.

PP populations will be used for summarizing CeD PRO results.

7.7.5 Assessment of the gluten-free diet (iVYLISA GIP stool test and urine gluten test)

In celiac disease, identification of gluten contamination is essential for the management of the disease and for the successful conduct of clinical trials. Contaminating gluten is a confounding factor in the evaluation of a potential therapeutic effect of any experimental

celiac-related medication, since histologic, serologic and clinical endpoints are heavily influenced by the presence of gluten in the diet.

In addition to measuring symptoms through patient reported diaries, Celimmune plans to use the iVYLISA GIP-S stool and urine gluten tests, gluten assays developed to detect inadvertent gluten consumption by measuring gluten immunogenic peptides (GIP) in faeces (Comino *et al*, 2012) and urine (Moreno *et al*, 2015).

The stool test detects gluten for up to seven days after consumption, and the urine test for 1-2 days. Testing will be done every two weeks – subjects should provide a urine and optional stool sample collected up to three days before or after the visit to the sites, in order to have a good probability of identifying dietary transgressors to enable correct data interpretation. Testing will be done at a central lab. For the purpose of the study, the stool test is considered negative when the average amount of gluten of a stool sample is <300 ng GIP/g stool sample.

iVYLISA GIP stool test and urine gluten test results (positive/negative) will be presented by visit and treatment group as well as listed.

PP analysis sets will be used.

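### SAP 7.9 treats on-study gluten compliance as a baseline subgroup; the separate models and the interaction test by compliance lose the protection of randomisation and can be biased

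*SAP*

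**What the plan says.** SAP 7.9 lists the subgroup factors that may be examined. Beside sex, site, and baseline histology, serology and biomarkers stands "Dietary transgressions (insufficient or excessive gluten consumption) based on serial iVYLISA GIP testing". It then states: "Separate models will be fitted for males and females, compliant and non-compliant subjects, and for each site". Significance of these three factors is to be judged from further fits, described as follows: "additional three models are fitted where compliance, sex and site and their interaction terms with treatment group, respectively, are included". The whole set is optional, depends on subgroups being of usable size, and may be restricted to the biopsy endpoints.

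Four other places bear on what compliance means here:

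- **Start of the challenge (section 3):** "Starting at Visit 2, subjects will switch to consume a daily total of approximately 2-4g of active gluten". Visit 2 is Week 2, after randomisation and the first dose.
- **Timing of the tests (section 7.7.5):** testing is every two weeks, and "subjects should provide a urine and optional stool sample collected up to three days before or after the visit to the sites".
- **Handling of non-compliers (section 3):** "those suspected of non-compliance to protocol specified gluten dosing will be counselled and allowed to continue in the study". They therefore remain available for these strata.
- **Effect of gluten on outcome (section 7.7.5):** "histologic, serologic and clinical endpoints are heavily influenced by the presence of gluten in the diet".

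Section 7.7.5 presents GIP results by visit and treatment group, in the PP sets.

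**The concern.** A subgroup comparison keeps the protection of randomisation only if membership is settled before treatment can act on it. Sex, site and the baseline factors in 7.9 meet that condition. Compliance with a challenge that begins at Week 2 cannot.

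The SAP itself supplies both links that make this matter. From treatment to compliance: "Attenuation of gluten-induced clinical symptoms" is a secondary endpoint (sections 2 and 7.6.2), and a subject with milder symptoms has less reason to leave the supplied gluten uneaten. From gluten to outcome: section 7.7.5 says intake heavily influences histology. If poor reactors cut back more often on placebo than on AMG 714, the placebo compliers are a milder group than the AMG 714 compliers, and the comparison is no longer like with like. The same holds among non-compliers and for the interaction.

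Section 7.9 gives no caveat and no method for a post-randomisation variable, while section 7.2 reads P below 0.05 as significant. A complier result in a gluten-challenge trial could easily be taken as the effect under full challenge.

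**Working it through.** **1. The plan's own figures.** Section 6 gives SD 36, differences of 40 and 35 points, 17 evaluable subjects per arm, and power of 88.8% and 79.3%. The standard error of a difference is 36 × √(2/17) = 12.35. The noncentrality parameters are 40/12.35 = 3.24 and 35/12.35 = 2.83. With 48 error degrees of freedom (three arms of 17) and two-sided 0.05, power is 88.8% and 79.3%, as stated. 17/(1 − 0.19) = 20.99, giving 21 per arm, also as stated. SD 36 and the 40-point effect are therefore a fair scale for the illustration.

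**2. Assumptions.** The SAP gives no compliance rates by arm and no link between reaction and injury. I assume:

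- 30% of placebo and 10% of AMG 714 subjects, those with the strongest reactions, cut back on gluten;
- reaction and VH:CD injury are jointly normal with correlation r = 0.3, 0.5 or 0.7, and SD 36 for the % change;
- only insufficient intake is modelled.

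**3. Compliers.** Removing the top fraction q of reactors lowers the mean standardised reaction of the rest by φ(z)/(1 − q), where φ is the standard normal density and z the cut point.

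- Placebo: 0.3477/0.70 = 0.497
- AMG 714: 0.1755/0.90 = 0.195

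The complier contrast (AMG 714 minus placebo, positive favouring the drug) shifts by −36 × (0.497 − 0.195) × r = −10.9r.

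| r | Shift | True 40 appears as | True 0 appears as |
|---|---|---|---|
| 0.3 | −3.3 | 36.7 | −3.3 |
| 0.5 | −5.4 | 34.6 | −5.4 |
| 0.7 | −7.6 | 32.4 | −7.6 |

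A simulation with 400,000 subjects per arm gave 36.7, 34.6 and 32.3 for a true 40, and −3.1, −5.4 and −7.4 for a true zero.

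**4. Non-compliers and interaction.** Mean standardised reaction among those who cut back is 0.3477/0.30 = 1.159 on placebo and 0.1755/0.10 = 1.755 on AMG 714. Their contrast shifts by −36 × (1.755 − 1.159) × r = −21.5r, or −6.4 to −15.0 points. The complier-minus-non-complier contrast, which the interaction tests, shifts by (−10.9 + 21.5)r = 10.6r, or about 3 to 7 points, with no true interaction.

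**5. Other assumed rates.** With no true effect and r from 0.3 to 0.5:

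| Compliant, placebo / active | Shift in compliers | Shift in non-compliers |
|---|---|---|
| 70% / 85% | −2.4 to −4.0 | −4.3 to −7.1 |
| 60% / 90% | −4.8 to −8.0 | −8.5 to −14.2 |
| 50% / 90% | −6.5 to −10.8 | −10.3 to −17.1 |
| 80% / 80% | about 0 | about 0 |

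With r = 0 the shift is also about 0 at every rate pair.

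**6. Against sampling error.** With the rates in step 2, 17 per arm leaves about 12 placebo and 15 AMG 714 compliers. The standard error is 36 × √(1/12 + 1/15) = 13.9 points, so a shift of 3.3 to 7.6 is 0.24 to 0.55 standard errors. At r = 0.5 and 17 per arm, a nominal 5% complier test with no true effect rejects 5.8% of the time at 70%/85% compliance and 8.5% at 60%/90%.

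**The case against.** The strongest reply is that little hangs on these analyses. They are optional, additional to the main analyses, and confined to histology. The primary ANCOVA in 7.6.1 has no term for compliance as used in 7.9. The arms are small enough that imprecision outweighs a bias of this size. All of that stands and limits the weight of the point. The condition on subgroup size is not a safeguard, though: it screens for numbers, not bias, and is more likely to remove the small non-compliant stratum than the complier estimate.

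A second reply is that results by gluten intake are a legitimate question in a challenge study. That also stands, and is why a descriptive display should remain.

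A reader might infer that these estimates are certainly biased, or that a drug with no histological effect would look beneficial. The SAP supports neither. Bias requires treatment to shift compliance and compliance to track prognosis; if either link is missing, it is about zero. Every unequal-compliance scenario above with a non-zero correlation moves the contrast against the drug. Section 7.9 also counts excessive intake as a transgression; this was not modelled and could act differently.

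**Conclusion.** The point holds as a risk of bias, not as demonstrated bias. Section 7.9 plans treatment-effect models and a significance test conditional on a variable known only after randomisation, which the SAP's own premises make plausibly dependent on treatment and related to outcome. It attaches no caveat.

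Under the 30%/10% assumption the complier contrast shifts by about 3 to 8 points against AMG 714, compared with planned effects of 35 to 40. Those rates, the correlations and the restriction to insufficient intake are assumptions, so neither size nor direction is established for this trial. It would be wrong to conclude that the primary result is compromised through this section, or that the sex, site and baseline subgroups share the fault. This is an inexpensive improvement to an exploratory section.

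**What to change.** **Section 7.9.** Remove compliance from the sentence on separate models and from the sentence on interaction models, leaving sex and site as they are. Present the histology endpoints by on-study compliance and arm as descriptive summaries, labelled as non-randomised comparisons and without treatment-effect p-values.

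**Section 7.7.5.** Tabulate GIP results by visit and arm in the ITT (all dosed) population as well as in the PP sets already planned. Under 7.2.3 the PP sets omit subjects who stop study drug before Week 6, so differential gluten intake may not be fully visible in them. Section 7.2 already provides all listings on the ITT population, so only a table is added.

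A subgroup based on GIP tests before the first dose would not replace this: active gluten starts at Week 2, so such tests cannot measure compliance with the challenge.

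The cost is SAP wording and one extra table. The downside is that one exploratory test becomes descriptive.
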